3.1. Inclusion Criteria

1. Age 18-65
2. Less than Bachelor's degree
3. Smoke >4 cigarettes/day for at least a year
4. Willing to smoke one flavor of cigarette during the trial (menthol or non-menthol)
5. Read and write in English
6. Able to understand and consent to study procedures
7. Plan to live in the local area for the next 8 months
8. Women not pregnant or nursing and taking steps to avoid pregnancy
9. No quit attempt in the past month and not planning to quit in the next 6 months (ensuring stability of smoking).
10. Ability to consistently receive phone calls over the next 8 months
11. Participants who become prisoners or otherwise subject to correctional supervision through probation, parole, home confinement, electronic monitoring, work release or other monitored, non-custodial supervision after signing the consent form.

Notes Related to Prisoner Participation

- The prisoner participant must be permitted by their probation/parole officer, court or other supervising authority to go to the research office visits, and the devices need to be programmed to reflect that additional time/place of travel. These issues will be resolved by the prisoner and their supervising authority on a case-by-case basis.

Rationale to include prisoners: Potential benefit of the subject (intent and reasonable probability of improving the health or well-being of the subject)

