3.2. Exclusion Criteria

1. College graduate
2. Currently pregnant or nursing
3. Systolic blood pressure greater than or equal to 160
4. Unstable or significant medical condition such as COPD or kidney failure that is likely to affect biomarker data
5. Use of non-cigarette nicotine delivery product in the past week (included cigars, pipes, chew, snus, hookah, e-cig, and marijuana)

6. Currently reducing or planning to reduce cigarette consumption in the next month
7. Use of smoking cessation medicine in the past month
8. History of difficulties providing blood samples; fainting, poor veins, anxiety, etc.
9. Regular use (more than weekly) of illegal drugs or prescription drugs used for non-medical purposes in the past 3 months or inpatient treatment for these in the past 6 months.
10. Uncontrolled serious psychotic illness (includes schizophrenia, bipolar disorder, eating disorder, and dementia) or inpatient treatment for a mental health condition in the last 6 months
11. Alcohol abuse that would hinder the participant's ability to participate
12. Significant medical condition i.e. stroke, MI, cancer in the last month
13. Other members of the household are currently participating in a trial related to reduced nicotine cigarettes
14. Taking an out of town trip or vacation in the next 8 months that will last 3 weeks or more or has major surgery planned in the next 8 months
15. Any other condition or situation that would, in the investigator's opinion, make it unlikely that the participant could comply with the study protocol
16. Participants who are prisoners at time of enrollment
17. Participants who become custodial inmates at any correctional facility after enrollment in the research.

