3.3. Early Withdrawal of Subjects

3.3.1. Criteria for removal from study

Participant withdrawal prior to randomization (Baseline Phase I and II)

These two phases are designed to identify participants who are not able or willing to comply with the full study protocol. During Baseline I, participants will smoke their own usual brand of cigarettes for 1 week. At Baseline II, all participants will be asked to smoke research cigarettes with a normal amount of nicotine. Participants who are removed during these two phases will be replaced prior to randomization until a total of 200 participants have been randomized (same for George Washington University).

Those who are not compliant with the study protocol prior to randomization for any of the following reasons will be withdrawn from the study **either during Baseline Phase I or Phase II:**

1. **Participant reports using any non-cigarette nicotine products at more than one visit.** Includes cigars, pipes, snuff, chew, hookah, electronic cigarette, marijuana, or any other illegal smoked substance, or any other nicotine containing product.

Those who are not compliant with the study protocol prior to randomization for any of the following reasons will be withdrawn from the study **during Phase II only:**

1. **Participant consumes more than 10% of cigarettes consumed are non-research cigarettes** in the 6 days prior to visit 3 only (Average cigarettes from day 15-20, e.g. 4 or more out of 30 cigarettes in 6 days for a 5 CPD smoker; 18 or more out of 180 cigarettes in 6 days for a 30 CPD smoker).
2. **Participant has reduced their cigarette consumption by more than 50% compared to baseline cigarettes per day** (when cigarettes per day are averaged over days 15-20) **because of non-compliance. This does not include situations of illness or other circumstances that would interfere with the participants' normal smoking behavior.**

Participant withdrawal at any point during the study if any of the following occurs:

1. **New pregnancy:** Participants who report a new pregnancy at any point during the study will be withdrawn or confirmed by urinary pregnancy test.

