Cigarette type:	Own Brand	Usual Nicotine Research Cigarettes	Reduced Nicotine Step 1	Reduced Nicotine Step 2	Reduced Nicotine Step 3	Reduced Nicotine Step 4	Reduced Nicotine Step 5	Variable
Nicotine content (mg/cigarette)[†]								
regular: RNC	Around 11mg	11.0	7.8	3.2	1.3	0.7	0.2	Variable
		9.9	7.0	3.4	1.4	0.7	0.2	
regular: UNC	Around 11mg	11.0	11.0	11.0	11.0	11.0	11.0	Variable
		9.9	9.9	9.9	9.9	9.9	9.9	

**As of the approval date of the June 7th 2017 version of the protocol, smokers entering the treatment choice phase will not be given the option to stay on research cigarettes.

[†]Nicotine contents are based on an estimated 0.7 g tobacco content per cigarette and nicotine concentrations (mg/g) from Richter et al. (2016)[36]

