7.2. Study Procedures

7.2.1. Baseline Phase I- Orientation/Assessment Visit and Visit 1 (Day 0)

1. Administer Project Screener 2
2. Informed Consent will be taken in a private clinic room in the CTSI.
 - a. Explain study protocol, use and description of cigarettes, and outcome measures.

Participant (P) will have adequate time to review the consent form and ask any questions. Two consent forms will be signed, one will be left at the clinic and one will be taken with the participant.

3. Give the P the Study Overview Participant Handout (uploaded in Supporting Documents named Study Overview Participant Handout)
4. Give pregnancy test for women childbearing age (have had a period in the past 12 months) and who have not had a hysterectomy for eligibility. Women will give a urine sample and the coordinator will perform a pregnancy urine test to see if it is positive or negative to confirm the eligibility criterion.
5. Complete medical history, NIDA drug screen, and concomitant medications forms and blood pressure measurement will be completed to confirm eligibility (all questionnaires (Q) are uploaded in Supporting Documents section).
6. Research staff will take heart rate (HR), weight, height, and waist:hip ratio measurements. Exhaled CO will be taken by the research coordinator with the Pico+ Smokylzer by blowing into a tube.
7. If P meets all inclusion criteria the coordinator will proceed with the rest of the baseline questionnaires below (all questionnaires are uploaded in Supporting Documents named Appendix of Coordinator entered Surveys and Appendix of Subject entered surveys):
 1. Demographics
 2. Tobacco Use History
 3. Butt out Q.
 4. Cigarette Details
 5. Nicotine Dependence Q.
 6. WI Prepare
 7. Cigarette Liking scales
 8. Revised MN Withdrawal Scale
 9. Questionnaire on Smoking Urges
 10. Centers for Epidemiological Studies (CESD)
 11. Perceived Stress Q.
 12. Kessler 6
5. Explain to P that they will smoke their current brand of cigarettes as usual for the next week. Compliance with the study protocol including not using other forms of tobacco or marijuana will be stressed. Participants will also be asked to honestly report any other tobacco or marijuana use at subsequent visits.

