These Ps will be offered an optional flexible smoking cessation treatment in which they will have the option to receive up to 11 weeks of short acting nicotine replacement therapy (gum or lozenges) at no cost and cognitive behavioral based smoking cessation counseling provided by study staff either in person or over the phone. Ps interested in quitting smoking must be willing to set a quit date one day before the week 22 visit (see Table 1 below). Ps will be given 6 day supply of the same research cigarette allocation that they received in Visit 8 to use until their quit date.

By this visit, some participants will have transitioned to smoking very low nicotine content research cigarettes. In order to select an appropriate nicotine replacement (NRT) dose, participants will be asked to quit smoking the day before their next visit (week 22). Participants will be encouraged to call the state telephone quit line and/or use the Freedom from Smoking (FFS) quit website (<http://www.ffsonline.org/>) to supplement the brief, in-person smoking cessation counseling sessions provided by study staff.

Table 1. Schedule of contacts for participants who choose to quit smoking during the Treatment Choice Phase 4

	Wk21 End randomized phase		Wk 22 Day 154		Wk 23 Day 161	Wk 24 Day 168	Wk 25 Day 175	Wk 26 Day 182	Wk 27 Day 189	Wk 28 Day 196	Wk 29 Day 203	Wk 30 Day 210	Wk 31 Day 217	Wk 32 Day 224	Wk 33 Day 231
In Person	X		X				X			X					

counseling session											
Telephone session			X	X			X			X	
Self guided session					X		X	X	X		X
Quit day		X									
Possible NRT disbursement			X			X			X		
End of NRT use											X

b. Participants who choose to switch back to their own brand:

These Ps will have to purchase their usual brand of cigarettes at their own cost and not be given any more research cigarettes. Ps will be given the Daily cigarette diary and be instructed to use this everyday to tally their cigarettes smoked. They will not be asked to bring back their usual brand cigarette packs.

10. If the Ps go back to their usual brand, the next study visit will be scheduled for 4 weeks later at approximately the same time. They will receive a print out of their next study visits.

11. If the Ps chose to make a quit attempt they will be seen one week later. They will receive a print out of their next study visits and phone calls.

17. Treatment Choice Phase- Extra Visits for Participants Who Choose to Make a Quit Attempt- Week 22 (Day 154, +7)

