- a. Ps who want to quit will complete the Smoking Cessation Q and given NRT. They will go over strategies to cope with any triggers/urges to quit. Participants could be given a refill of NRT (3 boxes of gum or lozenge) as deemed appropriate by the researcher according to the participant's NRT usage and withdrawal symptoms.
- b. Ps who switch back to their own brand will not be given any research cigarettes. P will be given the Daily cigarette diary and instructed to use this every day to tally any usual brand cigarettes smoked.

9. If the Ps go back to their usual brand, the next study visit will be scheduled for 8 weeks later at approximately the same time. They will receive a print out of their next study visits.

19. Treatment Choice Phase – Visit 11 (Day 231)- All Participants

1. Research staff will take BP, HR, and weight. Exhaled CO will be taken by the research coordinator with the Pico+ Smokylzer by blowing into a tube.
2. Give pregnancy test for women childbearing age (have had a period in the past 12 months) and who have not had a hysterectomy for eligibility. Women will give a urine sample and the coordinator will perform a pregnancy urine test to see if it is positive or negative to confirm the eligibility criterion.
3. P will give a blood sample taken by the Research staff in the CTSI clinic room.
4. P will give a urine sample.
5. Adverse events trigger questions.
6. Collect daily cigarette diaries from previous visit.
7. P will complete the following questionnaires
 1. Every Visit Form
 2. Concomitant medications
 3. Environmental Tobacco Smoke Q.
 4. Clinical COPD
 5. Revised MN Withdrawal Scale
 6. Questionnaire of smoking urges
 7. Centers for Epidemiological Studies (CESD)
 8. Perceived Stress Q
 9. Kessler 6
 10. Other Tobacco and Marijuana Use/Daily Cigarette Log (non-quitters only)
 11. Dependence Q (non-quitters only)
 12. Cigarette Liking Scale (non-quitters only)
 13. Butt Out Q. (non-quitters only)

8. No further counseling or NRT will be given to the participants.

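### All seven scheduled pregnancy tests are limited to women with a period in the past 12 months, so a woman who can conceive but has had none in that time is not scheduled for testing (cheap improvement, low severity)

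*Combined protocol and SAP*

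**What the plan says.** Seven of the eleven clinic visits in Section 7.2 include a urine pregnancy test: Visits 1, 3, 5, 7, 9, 10 and 11 (Days 0, 21, 63, 105, 147, 175 and 231). Each item carries the same filter: "Give pregnancy test for women childbearing age (have had a period in the past 12 months) and who have not had a hysterectomy".

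The rules that the tests serve carry no such filter:

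- Section 3.1, item 8 requires that women not be pregnant or nursing and that they take steps to avoid pregnancy.
- Section 3.2, item 2 excludes anyone "Currently pregnant or nursing".
- Section 3.3.1 states: "Participants who report a new pregnancy at any point during the study will be withdrawn or confirmed by urinary pregnancy test".
- Section 12 requires contraception from women of child-bearing potential, a term it does not define, and accepts hormonal methods.

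Section 14, on sharing results, describes the screening-visit test as given to female participants and does not mention periods.

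**The concern.** The filter treats 12 months without a period as inability to conceive. That fits natural menopause but not absent periods from another cause. A woman can meet Section 12 by using a hormonal method that has stopped her periods, and by the same fact fall outside the tests. That some hormonal methods do this is general clinical knowledge; the protocol does not say it.

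For such a woman, two stated safety rules (exclusion for pregnancy and withdrawal for a new one) have no scheduled test behind them. Self-report is also less dependable for her, because she has no missed period to alert her. What is at stake is earlier detection and withdrawal, before the study supplies more cigarettes or nicotine replacement.

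**Working it through.** The plan gives no figure to reproduce. The check is a count from the visit schedule in Section 7.2.

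**Inputs.** Test days are as listed above. Research cigarettes are handed out to every continuing participant at Visits 2 to 8 (Days 7, 21, 42, 63, 84, 105, 126), which is 7 times. At Visit 9 (Day 147) only those who choose to quit receive more: "Ps will be given 6 day supply of the same research cigarette allocation that they received in Visit 8". The Visit 9 text still offers 12 more weeks on research cigarettes, but the footnote to Table 2 in Section 7.1 withdraws this: "smokers entering the treatment choice phase will not be given the option to stay on research cigarettes". The counts follow the footnote.

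**Who is missed.** Suppose a woman's last period was *d* days before Day 0 and she has none afterwards. At test day *t* she meets the filter if *d* + *t* ≤ 365, that is, if *d* ≤ 365 − *t*.

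| Test day (visit) | Tested if *d* is at most | Hand-outs to every continuing participant at or after the test |
|---|---|---|
| 0 (1) | 365 | 7 |
| 21 (3) | 344 | 6 |
| 63 (5) | 302 | 4 |
| 105 (7) | 260 | 2 |
| 147 (9) | 218 | 0 (1 if she chooses to quit) |
| 175 (10) | 190 | 0 |
| 231 (11) | 134 | 0 |

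- *d* ≤ 365 − 231 = 134: all 7 tests.
- *d* from 135 to 365: between 6 tests and 1, with the later ones lost first. For example, *d* = 250 gives 4 tests (Days 0, 21, 63 and 105).
- *d* > 365: 0 of 7 under Section 7.2. If Section 14 is read literally, the Day 0 test is added, giving 1 of 7.

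**Which tests matter.** Four tests (Days 0, 21, 63, 105) precede a further hand-out of research cigarettes to everyone who continues. Day 147 does so only for those who choose to quit, which makes five for them. A woman loses one of the four only if *d* > 365 − 105 = 260, or one of the five only if *d* > 365 − 147 = 218. Day 175 can affect only later nicotine replacement. Day 231 is the last visit, where "No further counseling or NRT will be given to the participants".

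**Length of supply.** Research cigarettes are supplied for 147 − 7 = 140 days, or 140 + 6 = 146 days for those who choose to quit. Nicotine replacement, if chosen, can run from Day 154 to Day 231, which is 77 days or 11 weeks.

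**With a filter based on ability to conceive.** The same woman would have seven tests, at intervals of 21, 42, 42, 42, 28 and 56 days.

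**The case against.** The case against acting has four parts.

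- **Small consequence.** Participants already smoke ("Smoke >4 cigarettes/day for at least a year") and must have "No quit attempt in the past month and not planning to quit in the next 6 months". Section 12 describes the research cigarettes as no riskier than their own. Contraception is required, and withdrawal ends the study's supply but not the smoking. This stands, and it sets the low severity.
- **Unknown number.** The documents give no rate of women who can conceive but have had no period for 12 months. This stands too, so no estimate is offered.
- **Other routes to detection.** The screeners, medical history and adverse event trigger questions may ask about pregnancy, and Section 3.3.1 allows a urine test outside the schedule. Those forms were not available for review, so it cannot be said that detection depends on spontaneous report alone. Section 3.3.1 schedules no test of its own.
- **Section 14.** Read literally, it gives every woman the Day 0 test, the first check on eligibility. But that section is about sharing results, and the working procedure is Section 7.2.1. At most it restores one test and leaves the other six restricted.

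A reader might infer that any woman without periods during the study goes untested. The documents do not support that. The filter looks back 12 months and the study lasts 231 days, so many such women would still get some or all of the tests.

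**Conclusion.** The gap is real and follows from the text. The tests apply to a narrower group than the rules they serve, and the women left out include users of a type of contraception that Section 12 accepts. In the extreme case the loss is 0 of 7 scheduled tests (1 of 7 on the literal reading of Section 14). That requires no period in the 12 months before Day 0 and none afterwards. Women with a more recent last period lose fewer tests or none.

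The conclusion assumes that Section 7.2 is followed as written and that some enrolled women fit the description. A reader might go further and infer that pregnant women will be enrolled or kept on unnoticed, or that the trial's results are at risk. The documents support neither: the unseen forms may prompt detection, and nothing here touches power or the primary analysis. This is a cheap improvement of low severity, with practical value mainly at the tests that precede further study product.

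**What to change.** Replace the filter at the seven visits with: *all women who are not surgically sterile and not postmenopausal (12 months without a period and no other cause, such as hormonal contraception)*. The study's medical staff should confirm the wording. They should also say what counts as surgically sterile, because the present filter exempts only hysterectomy and a wider reading could drop tests that are now given.

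The change matters most at Days 0, 21, 63 and 105, and at Day 147 for those who choose to quit. Using it at Visits 10 and 11 is for consistency. At Visit 1 the test (item 4) comes before the medical history (item 5), so test whenever status is not yet established. Use the same definition for child-bearing potential in Section 12, and align Section 14 with it.

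The cost is a wording change and a few extra urine tests. The coordinator already performs the test, urine is already collected at all six later test visits, and medical history and concomitant medications are recorded at Visit 1, so the cause of absent periods can be checked there.

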7.2.2. Baseline Phase I- Visit 2 (Day 7)

1. Research staff will take BP, HR, and weight. Exhaled CO will be taken by the research coordinator with the Pico+ Smokylzer by blowing into a tube.
2. P will give a blood sample taken by the Research staff in the CTSI clinic room. Blood biosamples will be used to look at the following (some biomarkers will be analyzed in selected subgroups of collected samples):
 1. Nicotine metabolites (nicotine, cotinine, 3HC)
 2. Blood glutathione (GSH) and glutathionylated proteins (GSSP)
 3. Bilirubin
 4. Creatinine
 5. Hemoglobin
 6. High-sensitivity c-reactive protein (hs-CRP)
 7. Interleukin-6 (IL-6)
 8. DNA
3. P will give a urine sample. Urine biosamples will be used to look at the following (some biomarkers will be analyzed in selected subgroups of collected samples):
 1. Nicotine metabolites (nicotine, cotinine, 3HC)
 2. Tobacco specific nitrosamines (NNAL,NNK)
 3. Polycyclic Aromatic Hydrocarbons (1-Hydroxypyrene,)
 4. Oxidative stress biomarkers (8-OHdG, F2-isoprostanes)
 5. Creatinine
 6. Total solids
 7. VOC biomarkers (mercapturic acids)
 8. Menthol
4. Adverse events trigger questions (uploaded in Supporting Documents)
5. Collect daily cigarette diaries from previous visit.
6. Collect saliva samples and log from selected Ps.
7. Collect smoking topography device and cigarette butts from the selected Ps and remove data. Ask Device Log questions. Give the P the device back to use will be asked to use the device for the next two days after the clinic visit. If for some reason the participant was not able to complete collecting topography on the 2 days, we will ask them to make this time up at some point during the week. Give the P another set of cigarette butt collection bags to collect butts.
8. P will complete the following questionnaires
 1. Every Visit Form
 2. Tobacco and Marijuana use/daily cigarette log
 3. Concomitant Medications
 4. Audit- C (current alcohol consumption)
 5. Environmental Tobacco Smoke Q.
 6. Menthol Q.

7. Clinical COPD Q
8. Nicotine Dependence Q.
9. WI Prepare
10. Perceived Health Risks
11. Cigarette Liking scales
12. Revised MN Withdrawal Scale
13. Questionnaire on Smoking Urges
14. Centers for Epidemiological Studies (CESD)
15. Perceived Stress Q.
16. Kessler 6
17. Social Support Q.
9. P will be given research cigarettes that contain the normal amount of nicotine of conventional cigarettes and matched on the participants' menthol flavor preference (menthol vs. non-menthol). They will receive enough research cigarettes that will last them for 2 weeks at a 150% of their baseline reported cigarettes. They will be instructed to smoke as they normally do with the test cigarettes for the next 2 weeks.
10. The study coordinator will go over a study compliance protocol with the P. Compliance with not using non-research cigarettes, other forms of nicotine or tobacco, and marijuana will be stressed. The coordinator will complete the Compliance questionnaire that assesses the P's confidence in complying with the study procedures. Any confidence score 5 or lower will prompt the researcher to trouble shoot any problems with the P. This Q is uploaded in the Supporting Documents section.
11. Participants will be instructed to bring all cigarette packs (unopened, opened or empty) back to the study center at each study visit. This will allow the researcher to reconcile what was given out, smoked, and brought back and improve compliance.
12. P will be given the Daily cigarette diary and be instructed to use this everyday to tally their cigarettes smoked. They will also be asked to circle on their diary any non-research cigarettes that they may smoke so that we can record this at subsequent visits.
13. The selected Ps from Baseline I will be given saliva collection kits. P will be asked to perform the saliva collection protocol 4 times throughout the day before their next clinic visit and store them in the refrigerator until it is time to bring them to the clinic visit.
14. The next study visit will be scheduled for 2 weeks later at approximately the same time. They will receive a print out of their next study visits and phone calls.

7.2.3.

Baseline Phase II- Phone Survey 1 (Day 14)

1. Ask P the following questionnaires:
 - a. Tobacco and Marijuana use/daily cigarette log
 - b. Revised MN Withdrawal Scale
 - c. Questionnaire on Smoking Urges
 - d. Cigarette Liking Scale
 - e. Smoking Device Log (if applicable)
2. Remind P of next study visit, to complete and return the saliva samples (if applicable), and return cigarette packs (unopened, opened or empty) and topography device (if applicable).
3. P will receive \$10 for completing phone survey and will receive it in check form that is mailed to their house.

